**Footnotes for the Schedule of Events Table 5 (Follow-up Period for Patients Undergoing Joint Replacement Surgery)**

1. All available information for patients who undergo JR surgery must be collected, including placement of the prosthesis, healing of the surgical wound and the results of the histopathologic examination.
2. If it is not possible to obtain orthostatic blood pressure following JR then blood pressure and pulse should be recorded.
3. A Knee Society Score questionnaire for knee replacements or Harris Hip Score questionnaire for hip replacements.
4. In the event of more than 1 JR, imaging assessments should be repeated if it has been > 60 days since the joints were last imaged. If it has been ≤60 days since imaging assessments were completed, imaging assessments may be completed at the discretion of the investigator. An MRI may be requested by the imaging vendor after review of the X-rays.
5. Imaging will be done at week 4 if not done pre-operatively
6. Imaging may be performed on any joint following a report of clinically significant worsening or exacerbation of pain in the joint.

### 10.3. Criteria for Potentially Clinically Significant Values (PCSV)

Parameter	PCSV	Comments
Clinical chemistry		
ALT*	
>3 and ≤ 5 ULN and baseline ≤ 3 ULN*
 
>5 and ≤ 10 ULN and baseline ≤ 5 ULN
 
>10 and ≤ 20 ULN and baseline ≤ 10 ULN
 
>20 ULN and baseline ≤ 20 ULN
	
Enzyme activity must be expressed in ULN, not in IU/L.
 
FDA DILI Guidance July 2009.
 
Each category is calculated independently.
 
* At least one level is required; multiple levels are optional for phase 2/3 studies. If it is desirable to get the distribution across the different PCSV levels, additional shift table on ≤3, >3 to ≤5, >5 to ≤10, >10 to ≤20, and >20 category for baseline vs. post baseline may be provided

AST*	
>3 and ≤ 5 ULN and baseline ≤ 3 ULN*
 
>5 and ≤ 10 ULN and baseline ≤ 5 ULN
 
>10 and ≤ 20 ULN and baseline ≤ 10 ULN
 
>20 ULN and baseline ≤ 20 ULN
	
Enzyme activity must be expressed in ULN, not in IU/L.
 
FDA DILI Guidance July 2009.
 
Each category is calculated independently.
 
* At least one level is required; multiple levels are optional for phase 2/3 studies. If it is desirable to get the distribution across the different PCSV levels, additional shift table on ≤3, >3 to ≤5, >5 to ≤10, >10 to ≤20, and >20 category for baseline vs. post baseline may be provided

Alkaline Phosphatase	>1.5 ULN and baseline ≤ 1.5 ULN	
Enzyme activity must be expressed in ULN, not in IU/L.
 
FDA DILI Guidance July 2009.

Total Bilirubin*	
>1.5 and ≤ 2 ULN and baseline ≤ 1.5 ULN*
 
>2 ULN and baseline ≤ 2.0 ULN
	
Must be expressed in ULN, not in μmol/L or mg/L. Categories are cumulative.
 
FDA DILI Guidance July 2009.
 
* At least one level is required; multiple levels are optional for phase 2/3 studies. If it is desirable to get the distribution of significant level, additional shift table on ≤1.5, >1.5 to ≤2.0 and > 2.0 category for baseline vs. post baseline may be provided

Parameter	PCSV	Comments
Conjugated Bilirubin	(Direct Bilirubin >35% Total Bilirubin and Total Bilirubin >1.5 ULN) and (Direct Bilirubin <=35% Total Bilirubin or Total Bilirubin <=1.5 ULN) at baseline	Conjugated bilirubin dosed on a case-by-case basis.
ALT/AST and Total Bilirubin	(ALT >3 ULN and TBILI>2 ULN) and baseline (ALT <=3 ULN or TBILI <=2 ULN)  (AST >3 ULN and TBILI>2 ULN) and baseline (AST <=3 ULN or TBILI <=2 ULN)  (ALT >3 ULN and TBILI>1.5 ULN) and baseline (ALT <=3 ULN or TBILI <=1.5 ULN)  (AST >3 ULN and TBILI>1.5 ULN) and baseline (AST <=3 ULN or TBILI <=1.5 ULN)	FDA DILI Guidance July 2009.
ALT/AST and Total Bilirubin and ALP	(ALT >3 ULN and TBILI>2 ULN and ALP < 2 ULN) and baseline (ALT <=3 ULN or TBILI <=2 ULN or ALP >=2 ULN)  (AST>3 ULN and TBILI>2 ULN and ALP < 2 ULN) and baseline (AST <=3 ULN or TBILI <=2 ULN or ALP >=2 ULN)	FDA DILI Guidance July 2009.

Parameter	PCSV	Comments
CPK*	>3 and ≤ 10 ULN and baseline ≤ 3ULN* >10 ULN and baseline ≤ 10ULN	FDA Feb 2005. Am J Cardiol April 2006. Categories are cumulative. * At least one level is required; multiple levels are optional for phase 2/3 studies. If it is desirable to get the distribution of significant level, additional shift table on ≤3, >3 to ≤10, and > 10 category for baseline vs. post baseline may be provided
Creatinine	≥150 μmol/L (Adults) and baseline < 150 μmol/L >=30% change from baseline and <100% change from baseline ≥100% change from baseline	Benichou C., 1994 3 independent criteria
Uric Acid - Hyperuricemia - Hypouricemia	>408 μmol/L and ≤408 μmol/L at baseline <120 μmol/L and ≥ 120 μmol/L at baseline	Harrison - Principles of internal Medicine 17 th Ed., 2008. Two independent criteria
Blood Urea Nitrogen	≥17 mmol/L and <17 mmol/L at baseline	Two independent criteria
Chloride - Hypochloremia - Hyperchloremia	<80 mmol/L and baseline ≥ 80 mmol/L >115 mmol/L and baseline ≤ 115 mmol/L	Two independent criteria
Sodium - Hyponatremia - Hypernatremia	≤129 mmol/L and baseline > 129 mmol/L ≥160 mmol/L and baseline <160 mmol/L	Two independent criteria

Parameter	PCSV	Comments
Potassium - Hypokalemia - Hyperkalemia	<3 mmol/L and baseline $\geq$ 3 mmol/L  $\geq$ 5.5 mmol/L and baseline <5.5 mmol/L	FDA Feb 2005. Two independent criteria
Total Cholesterol	$\geq$ 7.74 mmol/L and < 7.74 mmol/L at baseline	Threshold for therapeutic intervention.
Triglycerides	$\geq$ 4.6 mmol/L and < 4.6 mmol/L at baseline	Threshold for therapeutic intervention.
Glucose - Hypoglycaemia - Hyperglycaemia	( $\leq$ 3.9 mmol/L and <LLN) and (>3.9 mmol/L or $\geq$ LLN) at baseline  $\geq$ 11.1 mmol/L (unfasted); $\geq$ 7 mmol/L (fasted) and < 11.1 mmol/L (unfasted); <7 mmol/L (fasted) at baseline	ADA May 2005. ADA Jan 2008.
HbA1c	>8% and $\leq$ 8% at baseline	HbA1c
Albumin	$\leq$ 25 g/L and >25 g/L at baseline	Albumin
hs-CRP	2 ULN or > 10 mg/L (if ULN not provided)	FDA Sept. 2005
Hematology		
WBC	<3.0 Giga/L and $\geq$ 3.0 Giga/L at baseline (Non-Black);  <2.0 Giga/L and $\geq$ 2.0 Giga/L at baseline (Black)  $\geq$ 16.0 Giga/L and < 16 Giga/L at baseline	Increase in WBC: not relevant.  To be interpreted only if no differential count available.

Parameter	PCSV	Comments
Lymphocytes	>4.0 Giga/L and <= 4.0 Giga/L at baseline	
Neutrophils	<1.5 Giga/L and >=1.5 Giga/L at baseline (Non-Black); <1.0 Giga/L and >=1.0 Giga/L at baseline (Black)	International Consensus meeting on drug-induced blood cytopenias, 1991. FDA criteria.
Monocytes	>0.7 Giga/L <= 0.7 Giga/L at baseline	
Basophils	>0.1 Giga/L <= 0.1 Giga/L at baseline	
Eosinophils	(>0.5 Giga/L and >ULN) and (<=0.5 Giga/L or <= ULN at baseline)	Harrison - Principles of internal Medicine 17 th Ed., 2008.
Hemoglobin	≤115 g/L and > 115 g/L at baseline for male; ≤95 g/L and > 95 g/L at baseline for Female. ≥185 g/L and <185 g/L at baseline for Male; ≥165 g/L and < 165 g/L at baseline for Female Decrease from Baseline ≥20 g/L	Three criteria are independent.  Criteria based upon decrease from baseline are more relevant than based on absolute value. Other categories for decrease from baseline can be used (≥30 g/L, ≥40 g/L, ≥50 g/L).

Parameter	PCSV	Comments
Hematocrit	$\leq 0.37$ v/v and $> 0.37$ v/v at baseline for Male; $\leq 0.32$ v/v and $> 0.32$ v/v at baseline for Female  $\geq 0.55$ v/v and $< 0.55$ v/v at baseline for Male; $\geq 0.5$ v/v and $< 0.5$ v/v at baseline for Female	Two Criteria are independent
RBC	Female $< 3$ Tera/L and baseline $\geq 3$ Tera/L $\geq 6$ Tera/L and baseline $< 6$ Tera/L  Male $< 4$ Tera/L and baseline $\geq 4$ Tera/L $\geq 7$ Tera/L and baseline $< 7$ Tera/L	Unless specifically required for particular drug development, the analysis is redundant with that of Hb.  Otherwise, consider FDA criteria.
Platelets	$< 100$ Giga/L and $\geq 100$ Giga/L at baseline  $\geq 700$ Giga/L and $< 700$ Giga/L at baseline	International Consensus meeting on drug-induced blood cytopenias, 1991.  Two independent criteria
Urinalysis		
pH	$\leq 4.6$ and $> 4.6$ at baseline  $\geq 8$ and $< 8$ at baseline	Two independent criteria

Parameter	PCSV	Comments
Vital Signs		
HR	$\leq 50$ bpm and decrease from baseline $\geq 20$ bpm $\geq 120$ bpm and increase from baseline $\geq 20$ bpm	To be applied for all positions (including missing) except STANDING.
SBP	$\leq 95$ mmHg and decrease from baseline $\geq 20$ mmHg $\geq 160$ mmHg and increase from baseline $\geq 20$ mmHg	To be applied for all positions (including missing) except STANDING.
DBP	$\leq 45$ mmHg and decrease from baseline $\geq 10$ mmHg $\geq 110$ mmHg and increase from baseline $\geq 10$ mmHg	To be applied for all positions (including missing) except STANDING.
Orthostatic Hypotension	Su SBP < 160 mmHg - SBP St – Su $\leq - 20$ mmHg DBP St – Su $\leq - 10$ mmHg Su SBP $\geq 160$ mmHg - SBP St – Su $\leq - 30$ mmHg DBP St – Su $\leq - 15$ mmHg	
Weight	$\geq 5\%$ increase from baseline $\geq 5\%$ decrease from baseline	FDA Feb 2007.

Parameter	PCSV	Comments
ECG parameters		Ref.: CPMP 1997 guideline. ICH E14 2005
HR	$\leq 50$ bpm and decrease from baseline $\geq 20$ bpm $\geq 120$ bpm and increase from baseline $\geq 20$ bpm	
PR	$\geq 220$ ms and increase from baseline $\geq 20$ ms	
QRS	$\geq 120$ ms & $< 120$ ms at baseline	
QTc	Absolute values (ms) >450 ms and baseline $\leq 450$ ms >480 ms and baseline $\leq 480$ ms >500 ms and $\leq 500$ ms at baseline  Increase from baseline Increase from baseline 30-60 ms Increase from baseline >60 ms	To be applied to any kind of QT correction formula.  $\Delta QTc > 60$ ms are the PCSA to be identified in individual subjects/patients listings.

#### 10.4. Protocol Deviations Excluding Patients from the PPS

[figure not shown]
Patients in violation of any of the following Inclusion/Exclusion Criterion will be excluded from the Per-Protocol Set.

- Inclusion Criterion 4: A clinical diagnosis of OA of the knee or hip based on the American College of Rheumatology criteria with radiologic evidence of OA (K-L score  $\geq 2$  for the index joint) at the screening visit, with the following definitions:
  - The index joint is defined as the joint with OA under evaluation for this study
  - A joint previously treated with JR surgery cannot be the index joint
  - A joint previously surgically modified within the past year cannot be the index joint (with the exception of cruciate ligament reconstruction surgery, patellar fracture repair surgery, or meniscal repair)
  - If a patient has a K-L score of  $\geq 2$  at more than 1 knee or hip joint, the index joint is the joint with the greatest WOMAC pain subscore at the screening visit
  - If 2 or more knee or hip joints have a K-L score of  $\geq 2$  and the same WOMAC pain subscore, the index joint is the joint with the greater K-L score
  - If 2 or more joints have a K-L score of  $\geq 2$ , the same WOMAC pain subscores, and the same K-L scores, then the investigator may choose 1 of these joints as the index joint
- Inclusion Criterion 5: Moderate-to-severe pain in the index joint defined as a WOMAC average pain subscale score of  $\geq 4$  at both the screening and randomization visits
- Inclusion Criterion 7: A history of at least 12 weeks of analgesics use for pain due to OA of the knee or hip, as defined by:
  - a) Inadequate pain relief from acetaminophen/paracetamol AND
  - Intolerance to or inadequate pain relief from opioid or tramadol therapy, unwillingness to take opioid or tramadol therapy for a medically acceptable reason, or lack of access to an opioid or to tramadol
- Exclusion Criterion 10: History of naproxen intolerance, or existence of a medical condition that is high risk for naproxen-associated complications (eg, high risk of gastrointestinal bleed, previous ulcer, condition requiring use of anti-coagulants or anti-platelet therapy, or acute coronary syndrome)

Additionally, patient who experience any of the Protocol Deviations listed below will be excluded from the Per-Protocol Set.

PDID	Description of Protocol Deviation
3.01	Baseline visit not performed
3.24	Screening visit was not performed
5.14	WOMAC patient assessment was not administered at Week 16 Primary Endpoint Analysis
8.04	Rescue medication administered during a protocol-prohibited period prior to scheduled visit during treatment period
8.05	Use of opioid medications anytime during treatment period
8.06	Use of non-protocol specified NSAIDs any time during the treatment
F.02	Confirmed treatment unblinding (in error)

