## 2. INVESTIGATION PLAN

### 2.1. Study Design and Randomization

The study consists of a screening period of up to 30 days, followed by a 7 to 10-day pre-randomization period. All randomized patients in this study will participate in Year 1, a 52-week randomized, double-blind, placebo- and naproxen-controlled treatment period. At the end of the 52-week treatment period, eligible patients have the option to continue for another 52-week double-blind naproxen-controlled treatment period called Year 2, followed by a 20-week follow-up period. Patients who do not consent, or are ineligible, for Year 2 will continue in a 20-week follow-up period. Patients are contacted by phone approximately 52 weeks after their last subcutaneous (SC) dose of study drug (Figure 1).

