#### **3.3. The Per Protocol Set (PPS)**

The per protocol set (PPS) includes all randomized patients from the mFAS who received all protocol required doses during the 16-week treatment period for the week 16 analysis and who do not have to be excluded due to relevant protocol violations. The PPS will be used to perform sensitivity analyses for the primary and selected secondary endpoints. Section 10.4 contains the list of protocol violations which lead to exclusion from the PPS and corresponding protocol deviation identification number (PDID). For the analysis of fasinumab 1 mg Q8W group comparing to the control groups, only the subset of patients concurrently randomized (i.e. after Protocol R475-OA-1611 Amendment 5 Global was implemented) will be included.

A PPS using the entire FAS is defined analogously to above and will be used for performing sensitivity analysis on the entire FAS.

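### SAP 10.4 gives the opioid, NSAID and rescue exclusions no Week 16 cut-off, so read literally, conduct after Week 16 decides who enters the Week 16 per-protocol analysis

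*SAP*

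**What the plan says.** SAP 3.3 builds the PPS from two conditions. The dosing condition carries a time limit: the patient must have "received all protocol required doses during the 16-week treatment period for the week 16 analysis". The deviation condition does not. It admits patients "who do not have to be excluded due to relevant protocol violations" and refers to SAP 10.4 for the list.

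SAP 10.4 applies that list without qualification: a "patient who experience any of the Protocol Deviations listed below will be excluded from the Per-Protocol Set". Three entries concern medication:

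- PDID 8.05: "Use of opioid medications anytime during treatment period"
- PDID 8.06: "Use of non-protocol specified NSAIDs any time during the treatment"
- PDID 8.04: "Rescue medication administered during a protocol-prohibited period prior to scheduled visit during treatment period"

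F.02 (erroneous unblinding) is also undated. PDID 5.14 is tied to the endpoint visit: "WOMAC patient assessment was not administered at Week 16 Primary Endpoint Analysis".

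SAP 2.1 describes "Year 1, a 52-week randomized, double-blind, placebo- and naproxen-controlled treatment period", and protocol 5.1.4 likewise runs the Year 1 treatment period from Day 1 through Week 52. SAP 5.7.1 uses the PPS for one of three sensitivity analyses of the Week 16 co-primary endpoints. SAP 3.3 defines a parallel PPS on the FAS. SAP 5.7.3 and 10.1 also use the PPS for the Week 44 WOMAC endpoints, with no separate deviation list or window.

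**The concern.** A per-protocol set for a Week 16 endpoint should depend on conduct up to Week 16. Take a patient who has every dose, no deviation and a valid WOMAC at Week 16, and who takes one prohibited NSAID around Week 40. Under the literal rule this patient leaves the Week 16 analysis, although the later tablet cannot have changed the Week 16 score. A comparable patient who leaves the study at Week 20 has little opportunity to deviate later and is more likely to be kept.

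Three things follow. Valid Week 16 data are discarded. Opioid, NSAID and rescue use are driven by pain, so the discarding plausibly depends on response and hence on arm. And two programmers could derive different sets from the same text for a pre-specified sensitivity analysis of the co-primary endpoints.

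**Working it through.** The documents give no PPS size, exclusion rate or PPS power, so there is no stated figure to reproduce. The check sets out the exposure window and then illustrates its effect under labelled assumptions.

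**Exposure (protocol Table 1; SAP Table 3).** Post-baseline clinic visits in Year 1 are Weeks 2, 4, 8, 12 and 16 (5 visits), then every 4 weeks from Week 20 to Week 52 (9 visits), 14 in all. The share after Week 16 is 9/14 = 64%. In days, with Week 16 at Day 113 and Week 52 at Day 365, it is (365 − 113)/(365 − 1) = 252/364 = 69%. The Week 1 phone contact is not counted. Counting it would add one visit before Week 16 and leave the 9 later visits unchanged.

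**Exclusions under an assumed constant, independent risk p per visit, with no dropout.**

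- Excluded by Week 16: 1 − (1 − p)^5
- Excluded by Week 52: 1 − (1 − p)^14
- Clean at Week 16 but removed later: 1 − (1 − p)^9

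| p | by Week 16 | by Week 52 | clean at Week 16, removed later |
|---|---|---|---|
| 1% | 4.9% | 13.1% | 8.6% |
| 2% | 9.6% | 24.6% | 16.6% |
| 3% | 14.1% | 34.7% | 24.0% |
| 5% | 22.6% | 51.2% | 37.0% |

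**Clustering within patients.** If p varies between patients as a beta distribution with mean 5% and first shape parameter 1 or 0.3 (assumed), exclusion by Week 52 falls from 51% to 42% or 32%. Removal among patients clean at Week 16 falls from 37% to 27% or 17%. The 30% dropout by Week 52 assumed in SAP 2.2 would also reduce these figures, because not every patient reaches all 14 visits.

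**Risk differing by arm (assumed 3% per visit on placebo, 1% on fasinumab).** Retention with a Week 16 window is 0.97^5 = 85.9% against 0.99^5 = 95.1%, a gap of about 9 points. With a Week 52 window it is 0.97^14 = 65.3% against 0.99^14 = 86.9%, a gap of about 22 points.

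**Later deviation depending on the Week 16 score.** The difference of 1.1 and SD of 2.4 come from SAP 2.2. The scores were simulated as N(0, 2.4) on placebo and N(−1.1, 2.4) on fasinumab. The probability of a deviation after Week 16 was logistic in the score, with assumed odds ratio 1.2 or 1.4 per point and an assumed base probability of 15% to 35% at the placebo mean. Only selection after Week 16 is modelled.

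| Odds ratio per point | Base | Difference among those kept | Retention gap between arms |
|---|---|---|---|
| 1.2 | 15% | about 1.08 | about 2 points |
| 1.4 | 15% | about 1.03 | about 4 points |
| 1.4 | 35% | about 0.98 | about 7 points |

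In the last row the SD among those kept also falls, from 2.40 to about 2.27, so the standardised effect goes from 1.1/2.4 = 0.46 to 0.98/2.27 = 0.43.

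**The case against.** The strongest reply is that SAP 10.4 never says 52 weeks. It implements SAP 3.3, whose defining sentence speaks of a 16-week period and excludes only for relevant violations, and PDID 5.14 is tied to Week 16. A 16-week reading is therefore open. This stands in part for 8.04, whose wording lacks any time. It is weak for 8.05 and 8.06, which say any time in terms, and the 16-week phrase in SAP 3.3 qualifies doses only.

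A second reply is that the wide window may be meant for the Week 44 endpoints, which use the same PPS. Deviations after Week 16 do matter there. But a window running to Week 52 fits neither Week 16 nor Week 44, and nothing in the SAP assigns windows by time point. It is also true that the PPS analysis repeats a repeated-measures model with imputation to Week 52, so later visits enter the model. That does not justify deleting a patient's valid Week 16 score.

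A third reply is that little rests on this set, and that is right. The PPS carries no alpha. The primary estimand applies regardless of rescue or prohibited medication, and the treatment-policy and tipping-point analyses do not use the PPS exclusions.

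A reader might go further and infer that the window extends into Year 2, because the rescue and opioid rules cover Year 2 and SAP 10.4 does not say Year 1. The documents do not support that: the PPS analyses serve Year 1 endpoints, and Year 2 efficacy is descriptive on the Year 2 safety set (SAP 3.4, 5.7.6).

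**Conclusion.** The point holds as a defect in the written rule. It is clear for 8.05 and 8.06 and arguable for 8.04. Read literally, conduct after the endpoint removes patients with valid Week 16 data from a Week 16 sensitivity analysis.

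How many is unknown. About 9% to 37% of patients clean at Week 16 is an illustration that rests on 1% to 5% independent risk per visit and no dropout; clustering or dropout lowers it. The effect on the estimate is modest, with 1.1 becoming about 1.08 to 0.98 under the assumed outcome-dependent deviation, together with unequal retention between arms.

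A reader might infer that the rule could manufacture support for fasinumab or undermine the primary result. Neither follows. Under these assumptions the shift is towards no effect, and the mFAS primary analysis and type I error control are untouched. The change is worth making because the rule is wrong for its stated purpose and cheap to correct.

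**What to change.** In SAP 10.4, state the deviation window for each PPS analysis time point, for both the mFAS-based and the FAS-based PPS:

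- **Week 16 analysis:** count 8.04, 8.05, 8.06 and F.02 only if they occur on or before the patient's Week 16 WOMAC assessment. For 8.04, use only scheduled visits up to and including Week 16.
- **Week 44 analyses:** count the same deviations up to the patient's Week 44 assessment. SAP 3.3 should also state the dosing condition for Week 44, which it now omits.

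The cost is a short addition to the SAP text and a date condition in the PPS derivation, using data already collected. It removes selection on conduct after the endpoint. It does not remove selection on pain-related deviations before Week 16, which any per-protocol set carries, so the PPS result should still be read as supportive only.

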- H2,11: There is no treatment difference between fasinumab 1 mg Q8W and placebo in the WOMAC physical function subscale scores averaged across Weeks 4, 8, 12 and 16 versus there is treatment difference in the WOMAC physical function subscale scores averaged across Weeks 4, 8, 12 and 16
- H2,12: There is no treatment difference between fasinumab 1 mg Q8W and placebo in the WOMAC pain subscale scores averaged across Weeks 36, 40 and 44 versus there is treatment difference in the WOMAC pain subscale scores averaged across Weeks 36, 40 and 44
- H2,13: There is no treatment difference between fasinumab 1 mg Q8W and placebo in the WOMAC physical function subscale scores averaged across Weeks 36, 40 and 44 versus there is treatment difference in the WOMAC physical function subscale scores averaged across Weeks 36, 40 and 44

The hypotheses H1,4, H1,5, H1,6, H1,7, H1,14 and H1,15 can be tested within the same analysis method used to test H1,1 as described in Section 5.7.1. Similarly, H2,4, H2,5, H2,6 and H2,7 can be tested within the same analysis methods used to test H2,1 as described in Section 5.7.1. Additionally, the treatment policy analysis, per-protocol analysis and subgroup analyses described in Section 5.7.1 for the primary endpoint can also be utilized for the hypotheses mentioned in this paragraph.

To test H1,2, H1,8 and H1,9, a method analogous to that used to test H1,1 in Section 5.7.1 can be utilized, replacing the respective WOMAC subscale score with the PGA score. Likewise, H2,2, H2,8 and H2,9 can be tested using a method analogous to that used to test H2,1 in Section 5.7.1, replacing the respective WOMAC subscale score with the PGA score and only using the subset of patients in the mFAS randomized after protocol amendment 5 for the analyses. The multiple imputation algorithm will be modified to resample values outside the range of the PGA score (0-5) in a manner similar to the primary analysis.

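### As written, SAP 10.4 removes patients from the Week 16 per-protocol set for analgesic deviations that can occur up to Week 52, after the endpoint has been measured

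*SAP*

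**What the plan says.** SAP 3.3 builds the PPS from mFAS patients who "received all protocol required doses during the 16-week treatment period for the week 16 analysis". A second condition deals with deviations and keeps only those patients "who do not have to be excluded due to relevant protocol violations". It leaves the list of violations to SAP 10.4, and it defines a parallel PPS on the FAS.

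SAP 10.4 states its rule without a time limit: "patient who experience any of the Protocol Deviations listed below will be excluded from the Per-Protocol Set". Three entries in that list concern analgesics:

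- PDID 8.04: "Rescue medication administered during a protocol-prohibited period prior to scheduled visit during treatment period"
- PDID 8.05: "Use of opioid medications anytime during treatment period"
- PDID 8.06: "Use of non-protocol specified NSAIDs any time during the treatment"

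Only one entry names the primary time point, PDID 5.14: "WOMAC patient assessment was not administered at Week 16 Primary Endpoint Analysis".

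Protocol 5.1.4 and SAP section 7 both run the Year 1 treatment period to Week 52. Protocol 7.2 sets the prohibited rescue window at the 24 hours before a scheduled visit.

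The PPS analysis is one of three sensitivity analyses of the Week 16 co-primary endpoints (SAP 5.7.1). SAP 5.7.3 allows "the treatment policy analysis, per-protocol analysis and subgroup analyses described in Section 5.7.1" to be used for further hypotheses, several of them at Week 44, and the table in SAP 10.1 lists the PPS for the Week 44 WOMAC endpoints.

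**The concern.** A per-protocol analysis at Week 16 should be decided by what happened up to Week 16. Here the dose rule respects that and the analgesic rules do not, so membership of the Week 16 set depends partly on the following 36 weeks.

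Two things are at stake. Valid, compliant Week 16 scores are discarded, which costs precision. The set is also selected on events after the outcome, and those events may be related to pain control and may differ between arms, which opens the result to selection bias.

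This analysis has a distinct job. The primary estimand and the treatment-policy analysis both disregard use of rescue or prohibited medication, and the tipping-point analysis deals with missing data. The PPS is the only one of the three sensitivity analyses that removes patients for prohibited analgesia, so its time window should match the endpoint it supports.

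**Working it through.** The documents give no PPS size and no deviation rate, so there is no stated figure to reproduce. The check is a reading of the rules, a count from the visit schedule, and two illustrations on stated assumptions.

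**1. The rules applied to one patient.** Take a patient with every dose to Week 16, a Week 16 WOMAC and no prohibited analgesic by then, who takes an opioid at Week 30.
- SAP 3.3 dose rule: met.
- PDID 5.14: not triggered.
- PDID 8.05: triggered, because Week 30 lies in the treatment period.
- Result: excluded from the Week 16 analysis.

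**2. How much of the window lies after the endpoint.** Inputs are the 52-week treatment period and the Year 1 schedule of events.
- Weeks: 52 − 16 = 36, and 36/52 = 69%.
- Post-baseline clinic visits to Week 16: weeks 2, 4, 8, 12 and 16, which is 5. After Week 16: weeks 20, 24, 28, 32, 36, 40, 44, 48 and 52, which is 9. So 9/14 = 64%. Each scheduled visit is an occasion for PDID 8.04.

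**3. Share of exclusions due only to later events (assumed rates, constant hazard).** With p16 the proportion having a listed deviation by Week 16, p52 = 1 − (1 − p16)^(52/16).

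| Assumed p16 | p52 | Later only (p52 − p16) | Share of p52 |
|---|---|---|---|
| 2% | 6.4% | 4.4 points | 68.5% |
| 5% | 15.4% | 10.4 points | 67.4% |
| 10% | 29.0% | 19.0 points | 65.5% |

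The share stays near two thirds across the range. The points lost depend entirely on the assumed rate.

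**4. Possible effect on the treatment difference (illustration).** From SAP 2.2: difference 1.1, SD 2.4. Assumed: Week 16 change is normal with mean 0 on placebo and −1.1 on fasinumab. The log-odds of a later deviation are ln(0.1/0.9) + ln(OR) × change, so the probability is 10% at zero change and rises with a worse score. Simulation used 2 million patients per arm.

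| OR per point | Deviating, placebo / fasinumab | Difference, all | Difference, later deviators removed |
|---|---|---|---|
| 1.0 | 10.0% / 10.0% | −1.102 | −1.103 |
| 1.2 | 10.7% / 8.9% | −1.106 | −1.086 |
| 1.4 | 12.2% / 8.9% | −1.101 | −1.047 |

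The largest shift is 1.101 − 1.047 = 0.054, about 5% of the difference (0.054/1.1), towards the null. Deviations driven by other mechanisms, such as adverse events, could act either way.

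**5. Week 44.** With the same set at Week 44, no dose after Week 16 is required, a Week 16 WOMAC is required (PDID 5.14), and deviations in the 52 − 44 = 8 weeks after the endpoint still exclude.

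**The case against.** The strongest reply is that a 16-week limit was intended. SAP 3.3 speaks of a 16-week treatment period and of relevant violations, and the entries in SAP 10.4 are short deviation-log labels. That is possible. But SAP 10.4 does not carry the limit over, two of its labels say any time, and PDID 5.14 in the same list shows that a visit was named where one was meant. If Week 16 was intended, the fix merely states it.

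A second reply is that imputation and the repeated-measures model run to Week 52, so one set has practical logic. This does not justify the Week 16 use: PPS patients have a Week 16 WOMAC, and later analgesia cannot alter it. Whole-period exclusion comes closer to suiting Week 44, overshooting by 8 weeks.

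A third reply, on size, stands. Some later deviators would already be out for missed doses, entry-criteria violations or no Week 16 WOMAC. Under the planning dropout rates of 15% to Week 16 and 30% to Week 52 (SAP 2.2), 15 of every 85 patients still followed at Week 16 leave by Week 52, which cuts later exposure. For any assumed rate, the points in step 3 are therefore gross figures and the net loss is smaller.

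A reader might also infer that any rescue use excludes a patient. It does not: PDID 8.04 covers only rescue within the prohibited 24 hours before a scheduled visit.

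**Conclusion.** The mismatch is real on the text. The Week 16 PPS drops patients with valid, compliant Week 16 data because of events after the endpoint. That follows from reading SAP 3.3 and 10.4 together and rests on no assumption about rates. It takes the window to be Year 1; PDIDs 8.04 to 8.06 do not say so, and the same medications are also restricted in Year 2.

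About 69% of the treatment weeks and 64% of the post-baseline clinic visits that can trigger exclusion come after Week 16. The two-thirds share of exclusions rests on a constant hazard and assumed rates.

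Two stronger conclusions are tempting and are not supported. One is that the sensitivity result is biased in a known direction, for instance by enriching placebo for good responders. The documents give no arm-specific rates, and the illustration shows a shift between nil and about 0.05 on a difference of 1.1. Open to selection bias, probably small and of uncertain direction, is as far as the evidence goes. The other is that the trial's main inference is weakened. The primary mFAS analysis, the alpha allocation and the sample size do not use the PPS, so only a supportive analysis is affected.

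**What to change.** In SAP 3.3 and 10.4, state that PDIDs 8.04, 8.05 and 8.06 count only when the event occurs on or before the analysed visit, which is Week 16 for the Week 16 PPS. If the PPS is kept for the Week 44 endpoints, apply the dose rule and these deviation rules through Week 44 for that analysis, and tie PDID 5.14 to the Week 44 assessment there. Make the change before database lock and unblinding, as SAP section 1 provides for revisions.

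For Week 16 this is a sentence of text. For Week 44 it adds a second PPS flag in mFAS and FAS versions. The dates are largely available: rescue use is recorded daily in the diary (Protocol 7.2), and start dates are collected for concomitant medications. Some of those dates will be partial or missing, so the cut-off will rely for some patients on the imputation rule in SAP 6.4.
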